Randomization and data collection	Consenting NHS doctors will be randomly assigned to two groups; 1 and 2. Participants in both groups will be asked to complete outcome measures at an initial baseline assessment, after which only participants in group 1 will access an 8-session, 10-week intervention (controlled phase). Next, group 2 will access the intervention during an 8-session, 10-week period (full implementation phase). Finally, we will collect further outcome measures 6 months after both groups have completed the intervention (follow-up phase). Following intention-to-treat principles, participants who do not attend any intervention sessions (and who do not formally withdraw) will be included in the study and will be invited to complete measures.	
Planned Sample Size	Minimum recruitment target of 180 participants, expecting 50% attrition, plus approx. 120 non-intervention participants.	
Data analysis method	 Trial data will be summarised using a CONSORT diagram and analyses will be based on intention-to-treat principles. The primary analysis will compare between-group differences in OLBI at 10-weeks, using ANCOVA adjusting for baseline OLBI. Secondary analyses: Between-group comparisons will be conducted at each measurement point using ANCOVA adjusting for baseline severity in the relevant outcome measure. Between-group and within-group effect sizes will be calculated using Cohen's d. Completion / dropout rates will be compared between groups using chisquare analysis. Predictors of dropout and treatment response will be examined as a secondary analysis using Elastic Net regularization Variability in burnout, wellbeing and job satisfaction will be examined across groups defined by job role and demographic characteristics using t-tests and appropriate non-parametric tests. Qualitative data will be analysed using thematic analysis. 	
Study Period	24 months (18 months active study period, plus 6 months analyses and dissemination)	

2. Background and rationale

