A recent examination of staff well-being in the English National Health Service (NHS) concluded that staff shortages related to occupational stress are linked with poor quality of care and poor patient experience (Sizmur & Raleigh, 2018), highlighting the widespread nature of burnout and its impact in the NHS. Burnout in the NHS is a system wide problem with Public Health England estimating the cost of staff absence due to poor health at £2.4 billion per annum. The NHS depends on having a healthy and productive workforce to deliver high quality patient care. The Boorman NHS Health and Well-being 2009 report found that 80% of staff felt that their health and wellbeing had an impact on patient care, but only 40% of staff felt their employer was proactively trying to improve their health and wellbeing. A recent survey of doctors found that around 97% of respondents felt that the NHS has a culture of seeing excessive stress and workload as the norm (Dominic, Gopal & Sidhu, 2021). The gravity of these issues has led to calls for the NHS to make the health and wellbeing of its staff a priority. Their 2015 report 'Work and wellbeing in the NHS: Why staff health matters to patient care' recognises the importance of staff health and wellbeing to both NHS organisations and patients and concludes that our healthcare system's greatest asset is the people who deliver it. As NHS services face unprecedented clinical demand, increasing financial pressures and a patient population with complex care needs, it is often the health and wellbeing of NHS staff that suffers.

Factor in the Covid-19 pandemic, and the outlook is even bleaker. Working during the pandemic has had a great impact on the wellbeing of doctors, resulting in an increase in burnout. Prior to the pandemic in 2020, 32% of doctors reported an impact on their wellbeing, in comparison to 42% of doctors who worked throughout covid (GMC,2021). The doctor's field of work is also something that has an impact on their risk of burnout (GMC,2021). Those with the highest risk of burnout were G.P.s (32%), followed by specialists (18%), doctors in training (11%) and finally SAS and LE doctors (7%).

For these reasons, and given the scale of the problem, the NHS Long Term Plan acknowledges the need to "support improved health and wellbeing of staff and management of sickness absence" (NHS England, 2019, pg. 87).

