4.1. Setting and participants

This study will include GMC registered doctors across the broad spectrum of medical specialties, from general practice in community clinics to specialist hospital-based outpatient and inpatient services.

Inclusion criteria

- GMC registered doctors from any areas of specialty and NHS healthcare services, including trainees on rotation in NHS services.
- Working either part-time or full-time in a clinical role.

Exclusion criteria

- Currently accessing or referred to any concurrent psychological intervention delivered by a mental health professional (this specifically refers to talking therapies for mental health problems).
- Doctors that are currently not in active clinical service at the time of recruitment (e.g., on sick leave, maternity leave or suspended for any reason).
- Doctors that work in a purely managerial, supervisory or educational role (e.g., not in clinical practice at the time of recruitment).

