4.3. Measures

Primary outcome measure

Occupational burnout will be measured using the Oldenburg Burnout Inventory (OLBI), a 16-item questionnaire designed to assess two facets of burnout, emotional exhaustion (OLBI-E) and disengagement (OLBI-D), including their cognitive and somatic aspects (Demerouti, Bakker, Nachreiner, & Schaufeli, 2001). For both dimensions, four items are phrased positively and four items are phrased negatively (reverse scored). Every item is scored between 1 (strongly agree) and 4 (strongly disagree), and item ratings are averaged into a single index (range = 1 to 4), where a higher score is indicative of increased burnout. Examples of positively and negatively phrased items are: "I can tolerate the pressure of my work very well"; "During my work, I often feel emotionally drained". A psychometric validation study applying

the OLBI in 2599 adults with a variety of professional backgrounds demonstrated high internal consistency (Cronbach's alpha = .74 to .76 for each subscale) as well as robust convergent, and discriminant validity (Halbesleben & Demerouti, 2005).

Secondary measures

- Participants will also be asked to report basic demographics (age, gender, ethnicity) and generic information about their job role and work setting (speciality, qualified vs. trainee status, hours of clinical work per week).
- The Warwick-Edinburgh Mental Well-being Scale (WEMWBS) is a 14-item questionnaire; each answered on a 1 to 5 Likert scale. Items cover different aspects of eudaimonic and hedonic mental wellbeing and are worded positively. Item scores are summed to produce a total score (range: 14 to 70), where higher scores indicate greater psychological well-being. Psychometric testing has indicated that this measure was valid, reliable and acceptable measure of well-being in adult respondents (Tennant et al., 2007); with good internal consistency (Cronbach's alpha = .89 to .91) and test-retest reliability (.81). This will be collected at each of the measurement points outlined in Figure 1 (weeks 0, 10, 20, 44).

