5.3. Secondary analyses

The analysis described above will be repeated at the 44-week follow-up. In addition, these analyses will be repeated at each of the post-intervention time-points illustrated in Figure 1 (weeks 10, 44), using the OLBI sub-domain scores (*exhaustion*; *disengagement*), the WEMWBS well-being measure, and the JDSS job satisfaction measure, controlling for baseline scores. These between-group comparisons will also be summarised using effect sizes (Cohen's d).

Post-intervention measures (weeks 10, 20, 44) will be compared to baseline measures (week 0) within each group, using paired-samples t-tests or an appropriate non-parametric test depending on the distribution of the data. Within-sample pre-post treatment effect sizes will also be computed using the method proposed by Minami et al. (2008).

Dropout will be defined as attending less than 4 (half) of the intervention sessions. We will examine predictors of dropout and treatment response (defined as reliable improvement in the OLBI measure), using all available baseline measures as candidate predictors. Reliable predictors of each of these outcomes of interest will be identified using a variable selection method called Elastic Net Regularization (Zou & Hastie, 2005) applied in separate logistic regression models for each dependent variable.

Additional secondary analyses will examine variability in burnout, wellbeing and job satisfaction across groups defined by their job role and demographic characteristics. Between-group comparisons will be made using t-tests (or Mann-Whitney U Tests if the data are not normally distributed).

Qualitative data collected via online surveys after all participants had the opportunity to access the intervention (week 20) will be analysed using thematic analysis (TA). TA will follow the 6-step phase of

analysis proposed by Braun and Clarke (2006). We will triangulate qualitative themes generated via the TA method with baseline survey data in order to explore if the themes vary according to job role (e.g., junior doctors, consultants, etc.) and setting (e.g., community vs. hospital services).

6. Ethical considerations

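### Section 5.3 names only two-group tests for comparing job-role and demographic groups, although several of these factors have more than two levels or are normally continuous

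*Protocol*

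**What the plan says.** Protocol section 5.3 sets out additional secondary analyses that will "examine variability in burnout, wellbeing and job satisfaction across groups defined by their job role and demographic characteristics". The method follows in the next sentence: "Between-group comparisons will be made using t-tests (or Mann-Whitney U Tests if the data are not normally distributed". No other test is named there for this objective. The section gives no rule for forming groups, no cut-points and no multiplicity control.

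The Synopsis describes the same analysis more loosely, "using t-tests and appropriate non-parametric tests".

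Section 4.3 lists what is collected. The demographics are age, gender and ethnicity. The job information is "speciality, qualified vs. trainee status, hours of clinical work per week". Section 4.1 recruits "GMC registered doctors across the broad spectrum of medical specialties". The qualitative paragraph of 5.3 illustrates job role with an open-ended list that begins with junior doctors and consultants. The background (section 2) reports burnout risk from an outside survey for four groups of doctors: GPs, specialists, doctors in training, and SAS and LE doctors.

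**The concern.** The t-test and the Mann-Whitney test each compare exactly two groups. Of the listed characteristics, only trainee status is written as a dichotomy. An analyst who keeps to the named tests has three ways to handle the rest: merge categories until two remain, cut age and hours at some point, or test every pair of categories.

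The first two discard information and depend on choices that could be made after seeing the data. The third raises the chance that some role or speciality appears to differ when none does. The sponsor would then report which groups of doctors are more burnt out on a weak footing. This is a stated method that does not match its variables, which is different from a detail left for later.

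**Working it through.** **1. The protocol's own figure.** The document gives no number for these comparisons. Its only calculation is the primary sample size in section 5.1. With f = 0.30, alpha 0.05, 80% power, two groups and one covariate, the noncentral F gives N = 90 (power 80.4%), and 90 / (1 − 0.50) = 180. Both stated figures reproduce and are not in dispute. I use 180, the minimum recruitment target, as the illustrative n.

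**2. Factors against the named tests.**

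| Factor | Form | Two-group test fits? |
|---|---|---|
| Qualified vs trainee | two levels as written | yes |
| Gender | usually two levels in analysis | usually |
| Ethnicity | normally more than two levels | no |
| Speciality | more than two levels (section 4.1) | no |
| Job role | more than two levels (open-ended list in 5.3) | no |
| Age, weekly hours | normally continuous; if banded, usually more than two bands | no |

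**3. Pairwise testing, one outcome.** The protocol sets no category counts, so k is an assumption. The number of pairs is m = k(k − 1)/2. If the tests were independent, the chance of at least one false positive at 5% would be 1 − 0.95^m. Pairs share groups, so simulation is the better guide (10,000 runs, equal groups, all means equal, two-sided 5%, n = 180 and n = 300).

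| k | m | independent | simulated, all pairs | one F-test |
|---|---|---|---|---|
| 3 | 3 | 14% | 12% | 5% |
| 4 | 6 | 26% | 20% | 5% |
| 5 | 10 | 40% | 28% | 5% |
| 6 | 15 | 54% | 36–37% | 5% |

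The simulated F-test rate lay between 4.6% and 5.2% throughout. The results barely changed between n = 180 and n = 300.

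**4. Pairwise testing, three outcomes.** Four groups give 6 × 3 = 18 tests for a single factor. Independence would give 1 − 0.95^18 = 60%, which is too high because the pairs share groups. Simulation at n = 180 gives about 50%, 44–45% and 39% for assumed between-outcome correlations of 0, 0.5 and 0.7.

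One F-test per outcome gives at most about 1 − 0.95^3 = 14.3%. Simulation gives 14.4%, 13.2% and 10.8% at the same three correlations. With six groups there are 15 × 3 = 45 tests, and the pairwise figure is about 67% to 69% at correlation 0.5.

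**5. Splitting a continuous variable.** A median split of a normal variable multiplies its correlation with the outcome by √(2/π) = 0.798. The effective sample size is therefore multiplied by 2/π = 0.637, about 64%. At n = 180, power ≈ Φ(atanh(r)·√177 − 1.96):

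- assumed r = 0.20: 77% unsplit, 57% after the split;
- assumed r = 0.25: 92% unsplit, 77% after the split.

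**The case against.** **The Synopsis is broader.** Its wording could admit Kruskal-Wallis. That stands and softens the point. But it names no parametric method for several groups and none for a continuous variable, and section 5.3 narrows the non-parametric option to Mann-Whitney.

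**Grouping may be left to the analysis plan.** Pooling and banding rules commonly are, and their absence is not held against the protocol. The test itself is fixed in the protocol, however, so an analysis plan using ANOVA or regression would depart from it.

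**The analysis is secondary and descriptive.** It compares non-randomised characteristics and touches no randomised comparison. This limits the importance. Neither 5.3 nor the objectives label these comparisons exploratory, and a two-group test cannot compare four groups jointly whatever the label.

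**Stronger readings that the document does not support:**

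- A reader might infer that the protocol plans to dichotomise or to run every pairwise test. It states neither; both are consequences of applying the named tests.
- The four groups in section 2 might be taken as the trial's role coding. They come from an outside survey, so four is only an illustration.
- Unadjusted comparisons might be called invalid because role, trainee status, age and hours are related. The protocol gives no figure for that, and it aims to describe variation without claiming to separate role from age. A multivariable model would also have to enter role, speciality and trainee status together, which overlap.

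**Conclusion.** The point holds for factors with more than two levels and for continuous factors. It does not hold for two-level factors, where the named tests are suitable.

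Under the illustration of four equal groups, all pairwise testing roughly quadruples the error rate for one outcome (about 20% against 5%). Over three outcomes it raises the rate to about 39% to 50%, against about 11% to 14% with one F-test per outcome. A median split costs about 36% of the information. These sizes rest on assumed category counts, equal groups, n = 180, no true differences, the stated range of outcome correlations and, for the split, normality.

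This is a minor-to-moderate correction to a secondary analysis. The week-10 primary ANCOVA and the sample size are unaffected.

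**What to change.** Replace the test sentence in section 5.3, and align the Synopsis line, along these lines:

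> Factors with two levels will be compared by t-test or, if the data are clearly non-normal, Mann-Whitney U test. Factors with more than two levels will be examined with one overall test per factor and outcome (one-way ANOVA, or Kruskal-Wallis), followed by Tukey- or Holm-adjusted pairwise contrasts. Age and weekly clinical hours will be analysed as continuous variables by linear regression or correlation. These comparisons are exploratory.

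The exploratory label is needed even after this change, because one overall test per factor does not control error across three outcomes and several factors.

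The cost is wording only, with the same data and software. The downside is that sparse categories, most likely in speciality and ethnicity, will need pooling. The pooling rule is best fixed before outcome data are examined.

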6.1. Considerations about informed consent

As the participants of this study will be NHS staff, this study does not strictly require NHS research ethics approval. However, it will require Health Research Authority (HRA) approval. We will nevertheless apply for review by an NHS REC, given that this is a clinical trial of a novel intervention, in order to obtain independent scrutiny of the study protocol and relevant recruitment materials and methodology. Our prior clinical trials involving NHS staff as participants have been reviewed by an NHS REC on this basis, given that interventions that affect NHS staff well-being indirectly also affected NHS patients' quality of care.

In order to obtain informed consent from healthcare professionals in line with good practice guidelines, we will take the following steps:

- Planned attendance by members of the research team to clinical team meetings will enable potential participants the opportunity to ask questions, raise concerns and discuss any aspects of the study that they wish to clarify. Potential participants will also be invited to contact a member of the research team if they have any further thoughts or questions after team meetings. Contact details will be provided as part of the Participant Information Sheet (PIS).
- Potential participants will be advised of their right to withdraw from the study at any stage and the right to request their data to be deleted from the study dataset. This will be explicit in the electronic participant information sheet, in the consent form, and will be explained to participants following notification of randomisation. Each participant will receive an electronic copy of the information sheet and consent form via email, for their records.

We will also be collecting fully anonymous data described in section 4.3. Our proposed method for aggregating and analysing fully anonymized data is congruent with the NHS information governance policy and good practice guidelines.

Potential for distress

Given the psychoeducational nature of the intervention, we do not envisage any potential for significant distress or adverse events. Nevertheless, participants will receive the contact details for the chief investigator in the information sheet, if they should wish to make a complaint or to raise any concerns about the intervention or conduct of the study. In the rare event that a participant should become distressed, they will be provided information by the research team about usual sources of psychological and or occupational health support available to employees in NHS Trusts.

Our team is highly experienced at conducting clinical trials of occupational burnout interventions, having involved over 700 participants in randomised controlled trials. To date, we have not encountered any serious adverse events in these studies, and we have been responsive to communicate with and support study participants who have contacted the research team directly with queries or concerns related to occupational wellbeing. This does not mean that adverse events could not potentially occur, but it clearly indicates that they are extremely rare in this context and type of study. In order to be responsive and to follow best practice guidelines for psychological research, we will:

1. Monitor email correspondence from participants on a weekly basis, with recorded delegation of monitoring to more than one member of the research team.

- 2. Have a senior and clinically-qualified member of the research team nominated to be a point of contact for research team members to consult with if queries and concerns arise during the course of the study. The co-directors of the research team will share this responsibility, both of whom are qualified psychotherapists.
- 3. Escalate any concerns (even if these are minor) raised by participants directly to the chief investigator within 24 hours.
- 4. Notify the sponsor organisations' R&D manager, the trial steering group, and the NHS REC about any formal complaints or adverse incidents recorded during the trial.

Risks to participants

See above section.

Risks to research team

See above section.

Potential for disclosure

See above section.

7. Dissemination

After the conclusion of data analysis, we plan to disseminate findings about this study using a variety of forms of communication, including:

- Scientific journal publications
- Newsletter in lay terminology
- NHS Trust communications newsletter and email

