4.4. Recruitment, study procedures and data collection

Participant recruitment process

- A principal investigator (PI) will be nominated at each of the participating trial sites, and this person will be responsible for promotion and recruitment tasks described below.
- A promotion and recruitment pack will include: (1) a brief newsletter and (2) a participant information video. These promotional materials will be disseminated to the workforce by the PI via local NHS management mailing lists, via organisational communication teams, and via NHS wellbeing teams, via NHS intranet front page, and via social media campaigns, and other appropriate pathways.

- The PI will also organise attendance at relevant team meetings (e.g., meetings of clinical leaders, managers) conducted remotely (e.g., using MS Teams) to promote the study. The PI may attend one or more of these promotional meetings, but may also delegate attendance to other members of the research team.
- The promotion and recruitment period will last up to twelve weeks. Promotion activities will commence once ethical approvals have been received. The formal electronic consent process (described below) will also be activated once ethical approval is in place. Potential participants will have the opportunity to contact the research team via email to clarify questions, if necessary.
- Promotional materials described above will contain a weblink to an electronic participant information sheet and consent form (when ethical approval has been given). This method will ensure that no paper copies can be lost or misplaced in the post, and will be an efficient way to gather informed consent using an industry-standard and secure online survey system. A sample text for the consent form that will be available electronically is provided in the Appendix. NHS managers and/or team leaders will not be involved in the consenting process, which will minimise administrative burden and the potential for selection biases or the application of undue pressure on potential participants.

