- Consenting participants will be randomly allocated to the online intervention groups. Allocation will be carried out by a NHS-based researcher who is independent of the core research team, using a computerized block randomization schedule. Randomisation will be communicated directly to study participants via email within one week of receipt of their electronic consent form. This email will contain further instructions on how participants can register onto an upcoming online workshop anonymously.
- The research team based at Rotherham Doncaster and South Humber (RDaSH) NHS Trust will inform the intervention facilitators when the recruitment target has been met, providing a list of consenting participants after the randomisation process has been concluded. This will ensure CPM facilitators will know how many participants to expect in each of the intervention groups, and how to address them (e.g., the list will include their first names and areas of specialty). A research assistant linked to the RDaSH research team will work closely with the CPM intervention facilitators to coordinate the organisation of the groups.

Organisation of the intervention groups

- Participants will access the intervention using video conferencing software.
- To allow flexibility and to accommodate different working patterns and shifts, participants will have the opportunity to attend one of several available groups (up to four groups will be running simultaneously) which occur throughout different days and times of the week. Participants will receive an email listing the available options, and they will select their preferred schedule.
- After participants select their preferred schedule (e.g., day/time for workshop attendance), details of the sessions, including weblinks, dates and times will be provided via email. Staff will be asked to attend the same session each week to ensure numbers are managed. However, we appreciate that shift patterns need to be accounted for so we will ask participants to notify the research team if they need to change their day on a selected week. We expect that those who agree to take part in the trial will complete eight sessions spread over ten weeks, however we understand that some will be unable to do so, therefore we will consider a participant as having dropped out of the trial if they miss four or more sessions.

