- Pseudonymised qualitative data will be collected using the same Qualtrics survey after all participants had the opportunity to access the intervention (week 20). The purpose of collecting this information is to obtain detailed feedback about the participants' experience of being involved in the study and attending the intervention. We expect that some participants will not have been able to attend any intervention sessions, and therefore we intend to ask them for qualitative feedback to enable us to understand barriers to participation. Therefore, qualitative data will be obtained both from those who attended at least one session of the intervention and those who did not. The qualitative questions are available in the qualitative survey question document.
- The final study dataset will be archived for potential future use in secondary analyses and to contribute to systematic reviews and meta-analyses. The study documents will be stored in a secure NHS network drive, only accessible to members of the research team, which is located behind RDaSH Firewall. This will ensure the security and adequate storage of research data, consistent with NHS and academic codes of information governance and data protection.
- All analyses will be carried out at a University site, and data will be held in a restricted-access drive. The study dataset will be held at RDaSH for 10 years after the conclusion of the study.
- The University of Sheffield will be a data processor, whilst RDaSH will remain the data controller. The University of Sheffield will store anonymised data for 10 years after the conclusion of the study.

5. Data analysis

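### Participant email to the research team is monitored once a week, so a concern sent that way can lie unread for up to 7 days; working-day checks would cut this to 3

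*Protocol*

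**What the plan says.** Section 6.1 of the protocol, under Potential for distress, lists four steps meant to keep the team responsive. Two matter here:

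- Step 1: "Monitor email correspondence from participants on a weekly basis", with the task delegated on record to more than one team member.
- Step 3: "Escalate any concerns (even if these are minor) raised by participants directly to the chief investigator within 24 hours".

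No shorter checking interval and no urgent route for the team mailbox is given. The start of the 24 hours is not stated.

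The same subsection gives a second route for complaints and concerns: "participants will receive the contact details for the chief investigator in the information sheet". It also makes the research team responsible for telling a distressed participant where psychological or occupational health support can be found.

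Several places show that people do contact the team:

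- Step 1 itself presupposes email from participants.
- Section 6.1 puts contact details in the information sheet alongside an invitation to approach a team member with further questions.
- Section 6.1 describes, from previous trials, "study participants who have contacted the research team directly with queries or concerns related to occupational wellbeing".
- Section 4.4 says, of the period before consent: "Potential participants will have the opportunity to contact the research team via email to clarify questions, if necessary".
- Section 4.4 also says "we will ask participants to notify the research team if they need to change their day on a selected week", and sends participants who forget their code to the team. The route for these two kinds of message is not stated.

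**The concern.** The plan pairs a fast escalation rule with a slow intake step. The 24-hour limit can govern only what happens once a message has been seen, and nothing makes the team look more often than weekly. A doctor who emails the team in distress could wait days before the message is opened. Pointing that person to support is the team's job, so this help waits as well as the notice to the chief investigator.

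What is at stake is the handling of participants' concerns, not the estimate of the intervention's effect. Expected risk is low. The programme is psychoeducational, and the protocol reports no serious adverse events among more than 700 participants in the team's earlier trials. It also accepts that adverse events remain possible, and its background section cites a review in which three of five studies supported a link between burnout and suicidal thoughts in doctors. A short intake delay is therefore worth having if it costs almost nothing.

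**Working it through.** The protocol states no total time from sending an email to escalation, so there is no figure of its own to reproduce. The delay follows from its two intervals.

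**Inputs**
- Monitoring interval: weekly, 7 days (section 6.1, step 1).
- Escalation limit: 24 hours, 1 day (section 6.1, step 3), taken to run from reading.
- Assumptions: the weekly check falls on a fixed day; emails arrive evenly over all seven days; a working-day check runs Monday to Friday.

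**Formulae.** The longest wait to be read is the longest interval between checks. With even arrivals, an email falls in an interval of length L with probability proportional to L and then waits L/2 on average. The mean wait is therefore ΣL² / (2 ΣL).

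**Weekly check (one interval of 7 days)**
- Longest unread: 7 days.
- Mean unread: 7² / (2 × 7) = 3.5 days.
- Longest time to the chief investigator, using the full 24 hours: 7 + 1 = 8 days.

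**Working-day check (intervals of 1, 1, 1, 1 and 3 days)**
- Longest unread: 3 days, over the weekend.
- Mean unread: (4 × 1² + 3²) / (2 × 7) = 13/14 = 0.93 days.
- Longest time to the chief investigator: 3 + 1 = 4 days.
- Over a four-day closure the interval becomes 5 days, so 5 + 1 = 6 days to the chief investigator.

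**Gain from the change**

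| | Weekly | Each working day |
|---|---|---|
| Longest unread (ordinary week) | 7 days | 3 days |
| Mean unread | 3.5 days | 0.93 days |

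The mean wait falls by 3.5 − 0.93 = 2.57 days.

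**The case against.** The strongest reply is that nothing here is wrong. The protocol cites no standard that weekly monitoring breaches. Its named route for concerns is the chief investigator's own contact details, which bypass the team mailbox. Step 1 does not forbid earlier reading, and a team that arranges sessions, sends reminders and handles changes of session day probably opens its email more often than weekly. Step 2 also gives team members a senior, clinically qualified person to consult.

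Much of this stands. It limits the point to one route and makes the full 7-day wait less likely in practice. It does not remove the point. Step 1 is the only commitment covering the team mailbox, participants are expected to write to it, and the consultation in step 2 and the signposting to support can begin only once the message has been read. If the team already reads its email daily, the protocol should say so.

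Two stronger readings are tempting and are not supported:

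- **That steps 1 and 3 contradict each other.** This would follow only if the 24 hours ran from sending, when a weekly check could not guarantee the limit. The protocol does not say that. On the ordinary reading, from when the message is read, the two steps are compatible, and the unstated start is a small gap in wording.
- **That a concern will reach the chief investigator only after the participant's next session.** Section 4.4 says "Staff will be asked to attend the same session each week to ensure numbers are managed", and the 8-day worst case exceeds 7 days. But the protocol ties no action by the chief investigator to the next session. The case needs an email sent just after a session, a check just missed and nearly all of the 24 hours used. The average delay, even with the full 24 hours, is 3.5 + 1 = 4.5 days. Eight sessions in ten weeks also leave room for longer gaps.

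**Conclusion.** The point holds as a modest improvement. The stated weekly interval lets a concern sent to the research team go unread for up to 7 days, 3.5 days on average, before escalation or signposting can start. The maximum assumes a fixed check day and no reading in between; the mean also assumes even arrivals. The delay does not apply to messages sent straight to the chief investigator. Given the low expected risk and that second route, this is desirable rather than necessary. It has no bearing on the sample size, the significance level or the primary analysis.

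**What to change.** In section 6.1, step 1, replace the weekly interval with a check of the team mailbox each working day. As a minor clarification, add to step 3 that the 24 hours run from the time the concern is read.

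The cost is two small wording changes and a little staff time each working day. Monitoring is already shared among more than one team member, so no new role is needed. If participants use email to change session day or recover a code, the mailbox has to be read more often than weekly in any case.
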